## Background:

Shared decision making (SDM) is a patient-centered and evidence-based model of clinical decision making. The feature of SDM is that clinicians work together with patients to plan the most appropriate and practical treatment for patients based on the patients' preferences and values. Recently, SDM has been implemented throughout the world to improve patients' health literacy and to have a better understanding of the treatment options, thereby improving patient-doctor communication and promoting the quality of care.

Lumbar degenerative disease is a critical public health issue in the aging society. SDM now becomes an important process because there is no consensus of evidence-based practice guidelines among the multiple complex treatment options for patients with lumbar degenerative disease. In addition, there is a lack of evidence to support the effect of patient decision aids (PDAs) to promote the quality of healthcare for patients with lumbar degenerative disease in Taiwan.

## Purposes:

This project has two purposes. The first purpose is to develop a multimedia interactive patient doctor communication system called the Taiwan Shared Decision Making for Lumbar Spine Treatment (Taiwan SDM LumST). The second and ultimate purpose is to conduct a cluster randomized controlled trial (cRCT) for the validation of the integrated SDM model and the effectiveness of SDM related outcome indicators.

## Methods:

In the first year of the 3-year project, investigators will develop the SDM communication teaching materials, PDAs, as well as the computerized platform of Taiwan SDM LumST through focus groups and consensus meetings. In the second to third year, investigators will recruit 130 patients with lumbar degenerative disease to participate in double blind cRCT in the affiliated hospitals of Taipei Medical University. Investigators will use Analysis of covariance (ANCOVA) and Pearson's chi-squared test were used to analyze the difference in outcomes between two groups. Using structural equation modeling to validate the factors of the SDM model and adopt generalized linear regression models with generalized estimating equations to examine the immediate, short-term, and long-term benefits of the Taiwan SDM

LumST in implementing the SDM model among patients with lumbar degenerative disease.

Expected results:

Investigators expect that the implementation of the Taiwan SDM LumST system will significantly improve the patients' decision preference, health literacy in the care of lumbar degenerative disease, and self-efficacy in SDM. It will also promote the health care quality and health outcomes (e.g., participation in SDM, quality of decisions, regret in decisions, health outcomes, and quality-of-life) in patients with lumbar degenerative disease.

Expected impacts on the society, economy, and academic developments:

The Taiwan SDM LumST will be an efficient and effective way to facilitate patient doctor communication and thereby, promote health outcomes and improve the quality of decisions made by patients with lumbar degenerative disease. No computerized interactive PDA of SDM system for patients with lumbar degenerative disease exists in Taiwan yet. Thus, our system would be the first in Taiwan for the lumbar degenerative population. Investigators hope that the Taiwan SDM LumST will not only contribute to academic research, but also facilitate SDM between patients and healthcare professionals in order to improve patient safety and enhance the quality of care in Taiwan.

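### Does recruiting through years 2 and 3 of a 3-year project leave the long-term comparison with early recruits only?

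*Combined protocol and SAP*

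**What the plan says.** All the timing information is in the Methods section of the combined protocol and SAP.

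- "In the first year of the 3-year project", the task is development: "investigators will develop the SDM communication teaching materials, PDAs, as well as the computerized platform of Taiwan SDM LumST".
- The trial follows: "In the second to third year, investigators will recruit 130 patients with lumbar degenerative disease".
- The longitudinal analysis uses "generalized linear regression models with generalized estimating equations", and its aim is "to examine the immediate, short-term, and long-term benefits of the Taiwan SDM" LumST system.

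The plan does not say how many weeks or months each of the three horizons lasts, when the last patient may enter, or when follow-up ends. The Purposes section names two aims, building the system and testing it in a cluster randomised trial. Neither aim mentions a long-term effect, which appears only as one of the three horizons in the Methods.

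**The concern.** Recruitment is the only activity named for years 2 and 3, and the project ends with year 3. On the plainest reading, enrolment can go on until the project closes. A patient who enters less than one long-term interval before that date cannot then give a long-term observation within the project.

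Two things would be at stake. The first is precision, since the long-term contrast would rest on fewer than 130 patients. The second is bias. If hospitals or clinicians opened at different dates, truncation would fall unevenly on clusters and perhaps on arms, and time of entry could track clinicians' growing familiarity with the platform. Outcomes such as decision regret and quality of life plausibly need time to show, so the long-term horizon is not trivial. A patient enrolled too late cannot be recovered afterwards.

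**Working it through.** **Inputs from the Methods section.** Project length 36 months; year 1 for development; trial window of 36 − 12 = 24 months; N = 130.

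**Inputs the plan does not give, taken as assumptions.** L, the long-term interval in months; A, the number of months over which enrolment actually runs; even accrual over A; follow-up ending at month 36.

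**Step 1: who can reach the visit.** The share able to reach it is min(1, (24 − L)/A).

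| L (months) | A = 24 | A = 18 | A = 12 |
|---|---|---|---|
| 1 | 23/24 = 96% (125) | 100% (130) | 100% (130) |
| 3 | 21/24 = 87.5% (114) | 100% (130) | 100% (130) |
| 6 | 18/24 = 75% (98) | 100% (130) | 100% (130) |
| 12 | 12/24 = 50% (65) | 12/18 = 67% (87) | 100% (130) |
| 18 | 6/24 = 25% (33) | 6/18 = 33% (43) | 6/12 = 50% (65) |

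The loss therefore runs from none to 75%, depending on two quantities that the plan leaves open. It is zero whenever enrolment stops at least L months before the end of year 3, and the wording allows that.

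**Step 2: cost in precision, for A = 24.** If patients were independent, the standard error would grow by the factor 1/√(1 − L/24):

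- L = 3: 1/√0.875 = 1.07
- L = 6: 1/√0.75 = 1.15
- L = 12: 1/√0.5 = 1.41

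The trial is cluster randomised, so these factors overstate the cost when the same clusters stay in and each loses patients evenly. With the design effect 1 + (m − 1)ρ, an assumed ρ of 0.05 and half of each cluster lost:

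- 10 clusters of 13: the design effect goes from 1.60 to 1.275 (m = 6.5), and √(2 × 1.275/1.60) = 1.26.
- 4 clusters of 32.5: it goes from 2.575 to 1.7625 (m = 16.25), and √(2 × 1.7625/2.575) = 1.17.

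The plan gives no intracluster correlation and no number of clusters, so these figures only illustrate the direction. Losing whole late-starting clusters would cost more.

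**Step 3: what closing enrolment early would buy.** Even accrual over 24 months is 130/24 = 5.4 patients a month. Keeping all 130 while closing 6 months early needs 130/18 = 7.2 a month; closing 12 months early needs 130/12 = 10.8. If the rate cannot rise, closing early enrols 5.42 × 18 = 97.5 or 5.42 × 12 = 65 patients. Those are the numbers who would have reached a 6-month or 12-month visit under full-window accrual (A = 24 in the table). The long-term contrast gains nothing, and the immediate contrast loses 32.5 or 65 patients.

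**The case for a change.** The strongest case for a change is that the favourable reading needs an enrolment cut-off, or follow-up beyond the project, that the plan nowhere states. Writing it down costs nothing, and if accrual does run to the end, late recruits are lost to the long-term contrast for good.

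The omission is real: the visit times, the last enrolment date and the end of follow-up are all absent. The step from omission to conflict does not hold. The Methods text sets a development year against the trial years; it does not say that enrolment continues to the last day of year 3 or that follow-up must stop there. Even on the unfavourable reading, the claim that only early recruits contribute is too strong for short intervals. With a 6-month visit, everyone enrolled in the first 18 of 24 months has data.

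The bias argument rests on staggered cluster openings, which the plan does not describe. Staggering would also have to differ by arm, or outcomes or effects would have to drift with entry date. Without that, a calendar cut-off is administrative missingness unrelated to outcome, and a generalised estimating equations analysis accepts unequal numbers of visits under that condition. Late recruits still contribute to whichever earlier horizons they reach.

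**Conclusion.** No change is called for. A conflict between recruitment and long-term follow-up is possible under one reading but is not established. Under that reading (even accrual over all 24 months, follow-up ending at month 36) the loss would be 12.5% of patients for a 3-month horizon, 25% for 6 months and 50% for 12 months. Under the equally available reading, in which years 2 and 3 hold the whole trial, it is zero.

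The gap is one of scheduling detail that investigators fill sensibly: they have to fix a visit schedule to collect the data, and that shows when enrolment should stop. The two possible remedies add little. Closing enrolment early is a trade-off between long-term data and total accrual, and only the sites' achievable rate can settle it. Limiting the long-term analysis to patients enrolled early enough selects the same patients who would have a long-term observation in any case. Reporting the number who contribute at each horizon, as is usual practice, will show any shortfall.

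This conclusion assumes that enrolment dates are not systematically different between arms. Nothing in the plan suggests that they are.

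### A cluster randomised trial is to be compared between arms by ANCOVA and Pearson's chi-squared, with no allowance for clustering, so the false-positive rate exceeds its nominal level whenever the ICC is positive

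*Combined protocol and SAP*

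**What the plan says.** The Purposes section gives the second and ultimate aim as "to conduct a cluster randomized controlled trial (cRCT) for the validation of the integrated SDM model and the effectiveness of SDM related outcome indicators". The Methods section repeats the design and gives the only sample-size figure: investigators will "recruit 130 patients with lumbar degenerative disease to participate in double blind cRCT in the affiliated hospitals of Taipei Medical University".

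For the comparison of the two arms, the Methods section says: "Investigators will use Analysis of covariance (ANCOVA) and Pearson's chi-squared test were used to analyze the difference in outcomes between two groups". It then names structural equation modelling to validate the model, and says the investigators will "adopt generalized linear regression models with generalized estimating equations to examine the immediate, short-term, and long-term benefits".

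The text does not state the unit of randomisation, the number or size of clusters, an ICC, a significance level, the unit on which GEE would be clustered, or which analysis is primary.

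**The concern.** Randomising clusters makes the cluster the independent unit. Patients in one cluster tend to resemble each other, and that shared variation adds to the variance of the difference between arms. ANCOVA on individual patients and Pearson's chi-squared have no term for it, so they take 130 patients as 130 independent pieces of evidence.

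A positive ICC is plausible here. The intervention is a patient-doctor communication system, and the expected outcomes include participation in shared decision making, decision quality and decision regret. All depend on the consultation, which patients in a cluster are likely to have in common. This is an inference, because the documents do not define the cluster.

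The error runs in one direction. P-values come out too small and confidence intervals too narrow for each outcome analysed this way. Ordinary differences between clusters could then be read as an effect of the system.

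**Working it through.** **Inputs**

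- From the Methods section: 130 patients, two groups, cluster randomisation, ANCOVA and Pearson's chi-squared.
- Assumed, because the documents are silent: two-sided 5% level; k equal clusters split evenly between arms; ICC from 0 to 0.10. For ANCOVA the ICC is the one that remains after covariate adjustment.

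The figure of 130 cannot be reproduced, since no power, effect size, SD or event rate, ICC or cluster count is given.

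**Formulas**

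- Mean cluster size: m = 130/k
- Design effect: DE = 1 + (m − 1) × ICC
- True error rate of a test that ignores clustering: 2 × [1 − Φ(1.96/√DE)]
- Effective sample size: 130/DE

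**Worked examples at ICC 0.05**

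- 4 clusters: m = 32.5; DE = 1 + 31.5 × 0.05 = 2.575; 1.96/√2.575 = 1.221; error rate 22.2%; effective sample size 130/2.575 = 50.5.
- 10 clusters: m = 13; DE = 1 + 12 × 0.05 = 1.60; 1.96/√1.60 = 1.549; error rate 12.1%; effective sample size 130/1.60 = 81.

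**True error rate of a nominal 5% test**

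| Clusters | m | ICC 0 | ICC 0.01 | ICC 0.05 | ICC 0.10 |
|---|---|---|---|---|---|
| 4 | 32.5 | 5.0% | 8.7% | 22.2% | 33.6% |
| 6 | 21.7 | 5.0% | 7.4% | 16.9% | 26.3% |
| 10 | 13.0 | 5.0% | 6.4% | 12.1% | 18.6% |
| 20 | 6.5 | 5.0% | 5.6% | 8.3% | 11.5% |
| 26 | 5.0 | 5.0% | 5.5% | 7.4% | 9.8% |

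**Check by simulation**

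Each cell had 8,000 trials with no true effect. Clusters were randomised, ANCOVA used one baseline covariate, and chi-squared was uncorrected with a 50% event rate. At ICC 0.05 the rejection rates were:

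| Clusters | ANCOVA | Chi-squared |
|---|---|---|
| 4 | 21.8% | 22.4% |
| 10 | 12.2% | 11.1% |
| 26 | 7.5% | 6.7% |

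At ICC 0 both tests rejected in about 4.4% to 5.5% of trials. The formula and the simulation agree closely.

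**What a valid analysis would deliver**

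Take a true effect of 0.5 SD (assumed) and ICC 0.05, and test with k − 2 degrees of freedom. With 4 clusters the critical value on 2 degrees of freedom is 4.30 and power is about 19%. With 10 clusters power is about 51%. If all 130 patients were independent, 65 per arm, it would be about 81%.

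**The case against.** The strongest reply is that the plan also names GEE, a standard method for clustered data. The Methods section does not rank its analyses, and the immediate benefit that GEE is meant to examine could be the between-arm effect itself. What stands is that the role of GEE is ambiguous. The link to time horizons suggests repeated measures within patients, but the text does not settle it. On either reading, ANCOVA and chi-squared remain the methods named for the difference between arms, and GEE does not correct them.

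A second reply is that this is a one-paragraph methods section. It does not say that ANCOVA will be run on individual patients without a cluster term, so the authors may simply have left the detail out. That is fair as to intent. But the plan commits to two named tests, and applied in their standard form they do not fit the named design.

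Third, the size is unknown. There is no excess at ICC 0, and with 26 clusters and ICC 0.01 it is trivial (5.5%). This stands as a limit on the size. It does not remove the mismatch, because the plan gives no ground for assuming the benign case. If the affiliated hospitals of one university are the clusters, their number may be small, and that is where the inflation is worst.

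Last, valid inference may leave little power. The calculation above confirms this, and it belongs in the cost of the fix.

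**Conclusion.** The concern holds. The design is cluster randomised, and the tests named for the comparison between arms make no allowance for that. For any positive ICC with more than one patient per cluster, their standard errors are too small and the false-positive rate is above nominal.

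The direction is certain under that condition, but the size is not. Over 4 to 26 equal clusters and ICCs of 0.01 to 0.10, a nominal 5% test has a true error rate between 5.5% and 33.6%. The 5% level, the cluster counts, the equal cluster sizes and the ICCs are all assumptions. The point should be settled before analysis, because it affects the validity of every outcome tested this way.

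**What to change.** Replace the ANCOVA and chi-squared sentence with inference based on the randomised unit:

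- **Continuous outcomes:** a linear mixed-model ANCOVA with arm and the baseline value (where one exists) as fixed effects, a random intercept for the randomised cluster, and Kenward-Roger or between-within degrees of freedom.
- **Categorical outcomes:** logistic GEE clustered on the randomised unit with a small-sample correction, or a cluster-adjusted chi-squared test.
- **Too few clusters for a model:** a t-test on baseline-adjusted cluster means with k − 2 degrees of freedom. With one cluster per arm this is zero and the test cannot be computed, so the plan should rule that design out.

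The plan should also name the cluster unit and the number of clusters, state the unit on which the GEE models are clustered, say which analysis is primary, and report the ICC with the results.

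The change itself costs wording and standard software, with no new patients or data. The price is wider confidence intervals and lower power. The investigators should recheck 130 patients with a design effect, because with few clusters the trial may need more clusters or patients to answer its question.

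### Does the one-clause plan for the structural equation model leave validation of the SDM model unsupported with 130 cluster-randomised patients?

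*Combined protocol and SAP*

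**What the plan says.** The Purposes section says that the cluster randomised trial is run "for the validation of the integrated SDM model and the effectiveness of SDM related outcome indicators". The Methods then assign the validation to one analysis in a single clause: "Using structural equation modeling to validate the factors of the SDM model". The same sentence goes on to "adopt generalized linear regression models with generalized estimating equations to examine the immediate, short-term, and long-term benefits", so generalised estimating equations (GEE) are tied to the effects of the system over time and not to the SEM.

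On size, the investigators will "recruit 130 patients with lumbar degenerative disease to participate in double blind cRCT in the affiliated hospitals of Taipei Medical University". The unit of randomisation, the number of clusters, the ICC and the basis for 130 are not given.

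The Expected results paragraph names eight constructs. Three are things the system should "significantly improve the patients' decision preference, health literacy in the care of lumbar degenerative disease, and self-efficacy in SDM". Five more are given as examples of quality and outcome measures: "participation in SDM, quality of decisions, regret in decisions, health outcomes, and quality-of-life". They are listed as expected effects. None is assigned to the SEM as a factor, an indicator or a path.

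**The concern.** Validation implies a result that could fail. If the model, time point and fit rule are not written down beforehand, all three can be chosen after the data are seen, and a stated aim of the trial then has no agreed test.

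The design adds a second worry. Patients in one cluster tend to resemble each other, and the standard chi-squared fit test assumes independent patients. If clusters were few and ignored, a correct model could be rejected too often, and any path from randomised arm could look significant too often. The only method named for correlated data belongs to another analysis, and 130 patients are not many for a model with several factors.

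**Working it through.** **The plan's own figure.** 130 cannot be reproduced, because no significance level, power, effect size, dropout or ICC is given. Under assumed inputs (individual randomisation, two means, two-sided 5%, 80% power), a standardised difference of 0.50 needs 126 patients. A difference of 0.55 needs 104, and with 20% dropout 104/0.8 = 130. Both are guesses, and neither concerns the SEM.

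**Model size.** Assume 3 indicators per factor, correlated factors and factor variances fixed at 1. With f factors and p = 3f indicators, free parameters = 2p + f(f−1)/2 and df = p(p+1)/2 minus that number.
- f = 3: 18 + 3 = 21 parameters, df 24, 130/21 = 6.2 patients per parameter.
- f = 5: 30 + 10 = 40 parameters, df 80, 3.3 per parameter.
- f = 8: 48 + 28 = 76 parameters, df 224, 1.7 per parameter.

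**Power of a close-fit test** (RMSEA 0.05 against 0.08, 5% level, N = 130, no clustering). The noncentrality is (N−1)·df·RMSEA². For df 24 it is 129·24·0.0025 = 7.74 under the null and 129·24·0.0064 = 19.81 under the alternative, and power is 0.34. It is 0.72 at df 80 and 0.98 at df 224. A path model on observed scores with df 5 to 20 has power 0.15 to 0.31. The answer runs from poor to very good, depending on a model that is not stated.

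**Clustering and the fit test.** Simulation: f = 3, loadings 0.7, factor correlation 0.4, 130 patients, maximum likelihood, 2,000 trials per cell. The entries are the proportion of correct models rejected at nominal 5%.

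| Clustering | Clusters | Clusters ignored | Pooled within-cluster fit |
|---|---|---|---|
| None | – | 0.062 | 0.068 |
| Item ICC 0.01 | 4 | 0.076 | 0.071 |
| Item ICC 0.01 | 10 | 0.060 | 0.057 |
| Item ICC 0.05 | 4 | 0.144 | 0.064 |
| Item ICC 0.05 | 10 | 0.092 | 0.059 |
| Item ICC 0.05 | 65 | 0.071 | 0.079 |
| Item ICC 0.10 | 4 | 0.411 | 0.066 |
| Item ICC 0.10 | 10 | 0.234 | 0.073 |
| Item ICC 0.10 | 65 | 0.075 | 0.080 |
| Factors only, ICC 0.05 | 4 | 0.062 | 0.066 |
| Factors only, ICC 0.05 | 10 | 0.054 | 0.052 |

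The excess needs three things together: clusters ignored, few clusters, and cluster effects acting on the items themselves with an ICC of about 0.05 or more. The within-cluster fit costs one degree of freedom per cluster (130 − 4 = 126, or 130 − 10 = 120).

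**Paths from arm.** With k clusters, the design effect is 1 + (130/k − 1)·ICC and the unadjusted false-positive rate is 2Φ(−1.96/√DE). At ICC 0.05 and k = 4, DE = 1 + 31.5·0.05 = 2.575 and the rate is 22%. At k = 10, DE = 1.60 and the rate is 12%. These rates cannot be set beside the fit figures as one scenario. Simulated with 4 clusters, using a three-item composite for the path:
- Item-level ICC 0.05: fit rejection 14%, arm false positives 14 to 15%.
- Factor ICC 0.05: fit rejection 6%, arm false positives about 18%.
- Item ICC 0.05 acting only through the factors: fit rejection 6%, arm false positives 28 to 29%.

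The direction is clear, but the size depends on a mechanism the documents do not describe. They also do not say that the SEM has an arm path at all.

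**Pooling the arms.** A shift of 0.5 SD on two unrelated factors, with equal arms, creates a covariance of 0.25·0.25 = 0.0625 and a correlation of 0.0625/1.0625 = 0.06. That is below the 0.17 detectable with 130 patients, so it is minor.

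**The case for a change.** The strongest case needs no ICC. Model validation belongs to the trial's main aim, it gets one clause, and with no fit rule it can be declared a success whatever the data show. A paragraph would settle this at no cost in data. The eight named constructs do not help, since none is given a role in the SEM and a larger model leaves fewer patients per parameter. The trial is set in affiliated hospitals. If the hospital were the unit of randomisation, the number of clusters could well be small, which is where ignoring them does harm.

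Much of this stands as a description. The specification is absent, and writing it down would be good practice. What does not stand is the step from absence to error. No stated rule or figure is shown to be wrong. The plan does not say that clusters will be ignored, and SEM can accommodate them. The constructs named under Expected results give the analyst candidates to work from. None of the results expected there rests on model fit, and the benefits of the system are assigned to other methods. The missing cluster count and the unexplained 130 concern the trial as a whole and are not faults of the SEM. Finally, the Purposes section speaks of validating the integrated model and the Methods of validating its factors. Reading these as the same thing is reasonable but not stated.

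**Conclusion.** No change to the plan follows. The SEM is under-described in a text of synopsis length, and that is a gap analysts can fill sensibly: choose the model from the named constructs, and fit it in a way that respects the clusters. The same data allow this, and in the simulated cases with 4 or 10 clusters the within-cluster fit kept rejection of a correct model at 5 to 7%.

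The possible harm is conditional. For an assumed three-factor, nine-indicator model with clusters ignored and an item-level ICC of 0.05, the fit test would reject a correct model in about 9% (10 clusters) to 14% (4 clusters) of trials, against 6% without clustering. At ICC 0.10 the figures are 23% and 41%. With 65 clusters they are 7 to 8%, and with an ICC of 0.01 they are 6 to 8%. The number of clusters, the ICC and the model are all assumptions. The documents show neither that 130 is too few for the SEM nor that it is enough. The conclusion is limited to the text supplied.

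### The trial is cluster randomised, but none of its between-group analyses (ANCOVA, chi-squared, GEE) is tied to the randomised cluster; with few clusters, false positives can run well above 5%

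*Combined protocol and SAP*

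**What the plan says.** The Purposes section of the combined protocol and SAP sets out to "conduct a cluster randomized controlled trial (cRCT) for the validation of the integrated SDM model". The Methods section repeats the design: investigators will "recruit 130 patients with lumbar degenerative disease to participate in double blind cRCT in the affiliated hospitals of Taipei Medical University".

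Methods then names the analyses that compare the arms. For outcomes in general: "Analysis of covariance (ANCOVA) and Pearson's chi-squared test were used to analyze the difference in outcomes between two groups". For effects over time, the investigators will "adopt generalized linear regression models with generalized estimating equations to examine the immediate, short-term, and long-term benefits".

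The document does not state:
- what was randomised (hospital, clinic or physician), how many clusters there are, or an ICC;
- the GEE grouping unit, variance estimator or reference distribution;
- any cluster term in the ANCOVA or chi-squared test;
- which analysis is primary.

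**The concern.** When clusters are randomised, patients in the same cluster share its influences, and the information about the arm effect is limited by the number of clusters. An analysis that does not know the randomised unit can report standard errors that are too small.

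ANCOVA and Pearson's chi-squared test, as ordinarily run, treat patients as independent. They are the methods assigned to the arm difference, with no restriction to a time point.

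The GEE could handle clustering, but naming it does not settle the matter. Two ordinary ways of running it fail when clusters are few:

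1. Grouped on patient, a natural choice for repeated visits. It handles correlation over time but ignores the cluster, and its standard errors are too small whenever the ICC is above 0.
2. Grouped on cluster with the usual sandwich variance and a normal reference. The sandwich is biased downward with few clusters, whatever the ICC.

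At stake is whether a reported benefit at the immediate, short-term or long-term assessment carries its nominal 5% error rate.

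**Working it through.** **Inputs.** From the document: 130 patients, two groups, cluster randomisation. Assumed, because not stated: 65 per arm, two-sided 5%, k = 4 to 40 equal clusters (m = 130/k patients each), ICC of 0.01, 0.05 or 0.10. The 130 cannot be reproduced, because no effect size, SD, power, alpha, ICC or cluster count is given.

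**Patients treated as independent, arm effect at one visit.** Design effect DE = 1 + (m - 1) x ICC. Reported SE / true SE = 1/sqrt(DE). Type I error = 2 x (1 - Phi(1.96/sqrt(DE))).

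Example, k = 4, ICC 0.05: m = 32.5, DE = 1 + 31.5 x 0.05 = 2.575, ratio 0.62, 1.96/1.605 = 1.221, type I error 22%.

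**Grouped on cluster, uncorrected sandwich, normal reference.** With equal clusters, reported SE / true SE is about sqrt(1 - 2/k), and the correctly scaled statistic is close to t on k - 2 df. Type I error is therefore P(|t| > 1.96 x sqrt(1 - 2/k)), which does not involve the ICC.

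Example, k = 4: 1.96 x 0.707 = 1.386 on 2 df, type I error 30%.

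| Clusters | Independent, ICC 0.01 | Independent, ICC 0.05 | Independent, ICC 0.10 | Cluster-grouped, uncorrected, any ICC |
|---|---|---|---|---|
| 4 | 9% | 22% | 34% | 30% |
| 6 | 7% | 17% | 26% | 18% |
| 10 | 6% | 12% | 19% | 12% |
| 20 | 6% | 8% | 12% | 8% |
| 40 | 5% | 6% | 8% | 6% |

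**Simulation check** (null trials, continuous outcome, single visit, near-equal clusters; 4/6/10/20/40 clusters). At ICC 0.05, patient grouping gave about 23/18/13/9/7%, slightly above the formula. Uncorrected cluster grouping gave about 30/18/12/8/6-7%, and much the same at ICC 0. At ICC 0, patient grouping was correct, at about 5%. Unequal clusters made uncorrected cluster grouping worse: 30-42/21-25/13-16/9-11/7-8%. For a binary outcome (50% event rate, ICC 0.05), patient grouping gave 22/17/11/7/5%.

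**Change between visits.** Under patient grouping, a constant cluster effect cancels and the error is 5-6%. If cluster effects vary over time (cluster autocorrelation 0.5, ICC 0.05), it is 24%, 13% and 7% with 4, 10 and 40 clusters.

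**Remedies under the same null.**
- Kauermann-Carroll variance with t on k - 2 df, continuous outcome: 4.5-5.5% with near-equal clusters, 4.7-7.3% with unequal ones. Binary outcome with unequal clusters: up to 8.4%.
- Mancl-DeRouen variance with t on k - 2 df: about 3% at 4 to 10 clusters, rising to 4-5% at 40, so conservative when clusters are few.
- Cluster-level t test: 3.5-5.9% in every complete-data setting; not examined under dropout.
- With k = 2, the cluster-grouped SE is estimated as zero and k - 2 = 0 df remain.

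Baseline-adjusted models and an exchangeable working correlation were not simulated. For ANCOVA, the ICC that counts is the one left after adjustment.

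**The case against.** The strongest reply is that this is an omission in a one-paragraph summary. GEE is a standard method for clustered data, and it is named inside a trial described as cluster randomised, so it may be the intended provision for clustering. Silence on a small-sample correction does not show that none is planned. Every input to the error rates except the 130 patients and the two arms is assumed, and the results run from no inflation to several-fold inflation.

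Much of this stands. A reader might infer that the plan groups the GEE on patient and so ignores clustering; the text names no grouping unit, so that is not supported. A reader might also infer that the hospitals are the clusters and therefore few. The phrase "in the affiliated hospitals of Taipei Medical University" gives the setting, not the randomised unit, and no count. Nor do the documents support saying that this trial's false-positive rate is 20% or 30%.

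The reply does not cover the ANCOVA and chi-squared tests, which have no clustering mechanism as named. Nor does it make the GEE safe: if clusters are few, grouping on the right unit with default software settings still inflates the error. A document that goes as far as naming its methods can say in two sentences which unit they respect.

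**Conclusion.** The concern holds as a conditional one. No between-group analysis is tied to the randomised cluster. Two named tests have no cluster term, and the GEE is left open between valid and invalid versions.

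The size depends on the cluster count and, where patients are treated as independent, on the ICC; neither is stated. At 4 to 10 clusters and ICC 0.05, the error is roughly 12-30% against a nominal 5%. At 20 it is 8-9%, and at about 40 it is 6-7%, which is small. Treating patients as independent does no harm if the ICC is 0. Under patient grouping, a between-visit change is affected only if cluster effects vary over time. Because no primary analysis is named, the weight of any one of these tests in the trial's conclusion is unknown.

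**What to change.** 1. State the randomised unit and the number of clusters.
2. Group the GEE on that unit, with patients and visits nested in it. Pre-specify one bias-corrected sandwich (for example Kauermann-Carroll or Mancl-DeRouen) with a t reference on (clusters - 2) df, and estimate the arm effect at each time point from that model.
3. Replace the unadjusted ANCOVA and chi-squared tests with estimates from that model or with cluster-level comparisons.
4. If there are about 6 or fewer clusters of unequal size, pre-specify a cluster-level analysis: one mean or proportion per cluster at each time point, compared by a t test on (clusters - 2) df.
5. If there are only two clusters, report the arm comparison as descriptive.

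The text change is small; the cost is apparent precision. The 95% half-width is t(k - 2) x sqrt((4/130) x DE) in SD units. For 4 clusters at ICC 0.05 this is 4.303 x sqrt(0.0308 x 2.575) = 1.21 SD. For 4/6/10/20/40 clusters it is 1.21/0.69/0.51/0.42/0.37 SD, against 1.96 x sqrt(4/130) = 0.34 SD if patients were independent. Power for a 0.5 SD effect falls from 81% to 19/34/51/67/75%. The design imposes most of this loss, and the trial's expected precision should be restated accordingly.

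The cluster-level t test weights clusters equally. It therefore targets a cluster-average effect and loses power when clusters are many and unequal (48% against 63% for the corrected GEE at 20 clusters, 0.5 SD effect), which is why it is proposed only for few clusters.
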